
The investigator team will be notified by the MICU attending after each participant enrollment, so one of the team members will present to MICU to collect the data prospectively in a standardized Data Collecting Sheet (DCS) by using REDCap and all protected health information (PHI) will be de-identified. As regards the control group, an E-research request will be submitted to provide a list by

all the consecutive adult patients admitted to FV-MICU with a diagnosis of DKA in the period between January 1st 2019 till the date of IRB approval. Prespecified sample size and matched in basal patient characteristics and DKA severity will be selected as the control group. Data will be collected retrospectively for the control group and will be recorded directly into the DCS in RedCap. Clinical outcomes will be compared between the intervention and control groups. The primary outcome includes time to anion gap closure ($AG \leq 12$). Secondary outcomes include hospital Length Of Stay (LOS), ICU LOS, total IVII dose, the incidence of transitional failure (defined recurrence of DKA after initial IVII discontinuation within 24 hours and requiring reinitiating the IVII), the incidence of hyperglycemia (> 180 mg/dL) and hypoglycemia (defined as ≤ 70 mg/dL, <54 , <40) during 24 hours from Insulin Glargine administration.

B. Definition of main exposures and outcomes:

Diagnosis of DKA will be made by ICD-10-CM code E10.10, E11.10, or meeting the ADA definition; $BG \geq 250$ mg/dl, $AG > 12$, and positive Ketones in serum or urine

DKA classification as the following table from ADA:

	Mild (plasma glucose >250 mg/dl)	Moderate (plasma glucose >250 mg/dl)	Severe (plasma glucose >250 mg/dl)
Arterial pH	7.25–7.30	7.00 to <7.24	<7.00
Serum bicarbonate (mEq/l)	15–18	10 to <15	<10

For the hyperglycemia analysis, patients will be compared in the following categories according to their mean or median (depending on the normality of the data distribution) blood glucose throughout the hospital stay:

- Mean/median BG <80 mg/dL
- Mean/median BG 81-100 mg/dL
- Mean/median BG 101-140 mg/dL
- Mean/median BG 141-180 mg/dL
- Mean/median BG > 180 mg/dL'
- Mean/median BG > 240 mg/dL

Hypoglycemia will be defined by three categories:

- any glucose level below 70 mg/dL
- any glucose level less than 54 mg/dL
- any glucose level less than 40 mg/dL

For Time of Anion Gap Closure (TAGC) will use the ADA definition: $AG \leq 12$ mEq/L

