Transitional failure will be defined as the recurrence of DKA ($BG \geq 250$ mg/dl, $AG > 12$, and positive Ketones in serum or urine) after initial IVII discontinuation within 24 hours and requiring reinitiating the IVII.

C. Study Population

Intervention vs Control group

- Intervention group: All consecutive adult patients getting admitted to FV- MICU and meet the inclusion criteria and accepted to receive insulin glargine early as per the protocol. They will receive insulin glargine 0.4 unit/kg within 4 hours from initiating the IV Insulin Infusion, as per the Cleveland Clinic DKA protocol.
- Control group: prespecified and matched sample size, consecutive adults who admitted to FV-MICU with a diagnosis of DKA in the period between January 1st 2019 till the IRB approval date and didn't receive basal insulin before AG closure.

Inclusion criteria:

- Age \geq 18 years old
- Meet DKA definition as above
- Having the capacity to sign Informed consent

Exclusion Criteria

- IV insulin infusion initiated more than 4 hours.
- Persistent hypotension (SBP<80 mmHg despite receiving 1000cc normal saline).
- Require Vasopressor
- Acute Coronary Syndrome
- Pregnant
- End-stage renal disease
- Unwilling to consent to participate in the trial
- Currently under police custody
- Transferred from another hospital
- Require emergent surgery
- Alcoholic Ketoacidosis

Study Variables:

General Informations:

- Patient name
- MRN
- Age
- Sex (Male, Female, Others)
- Race (White, Black, Asian, Other)
- Ethnicity (Hispanic vs. Non-Hispanic)
- Weight on admission (kg)
- BMI (Kg/m²)
- Height (cm)
- Date of Hospital admission
- Date of ICU admission

- Date of DKA diagnosis (MM/DD/YY)
- Precipitating cause of DKA
 - Noncompliance
 - New-onset
 - Infection
 - Cerebrovascular accident
 - alcohol abuse
 - pancreatitis
 - Drugs
 - Others

Past Medical history

- Type of diabetes:
 - Type 1 DM
 - Type 2 DM
 - Cystic fibrosis-related diabetes
 - Steroid-induced diabetes
 - Other or no clear diagnosis
- Known diagnosis of other major medical comorbidities (CAD, CHF, HTN, COPD, asthma, liver disease, CKD, cancer, other)
- On Renal Replacement Therapy (Y/N)
- Using Basal insulin at home (Yes/No/ unknown)
- If previous point answer is yes check the corresponding insulin type and write the dose: (Glargine, Detemir, Degludec, NPH, Continuous Insulin Pump) (dose: IU)
- Home total basal insulin dose (units)

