- Non-insulin antihyperglycemics taken at home prior to admission, including the type
 - Sulfonylureas
 - Thiazolidinediones
 - Dipeptidyl peptidase-4 (DPP-4) inhibitors
 - Biguanides
 - Glucagon like peptide-1 (GLP-1) analogues
 - Sodium-glucose transport protein 2 (SGLT2) inhibitors
 - Meglitinides
 - Alpha glucosidase inhibitors
 - Amylin analogues
- History of immunosuppression (history of cancer, HIV or auto-immune disease or organ transplant, chronic steroid)

Initial Laboratory values:

- Anion gap (mEq/L)
- Bicarbonate (mEq/L)
- Glucose (mg/dL)
- Beta-Hydroxybutyrate (mmol/L)
- Ketones in the urine (Y/N/Unknown)
- HbA1c %
- Lactate (mmol/L)

Intervention and outcomes:

- IV insulin infusion starting time
- Insulin glargine administration time
- Anion Gap closure time
- IV insulin discontinuation time
- Number of hours of IVII
- Total IV insulin infusion has been given
- Total IV insulin/weight
- Total IV fluid during DKA management
- Date of discharge from ICU
- Date of discharge from hospital
- Hospital Length Of Stay (days)
- ICU LOS (hours)
- Transitional failure (recurrence of DKA)?

Hypoglycemia Events

- Hypoglycemia event within 24 hrs from glargine
- Time of the hypoglycemia
- How many hours after the glargine administration?
- Severity
- How it has been treated

Hyperglycemia Events

- Hyperglycemia Event after IVII discontinuation by 24 hours (Y/N)
- time of the hyperglycemia event
- Severity of hyperglycemia
- How many hours after IVII discontinuation

D. Outcomes

Primary outcome: Time to anion gap closure (hours).

Secondary outcomes:

- Hospital Length of stay (days)
- ICU length of stay (hours)
- Total IV insulin infusion dose (International unit)
- Incidence of transitional failure (percentage).
- Incidence of hyperglycemia (> 180 mg/dL) during 24 hours from Insulin Glargine administration (percentage).
- Incidence of hypoglycemia (defined as ≤ 70 mg/dL, <54, <40) during 24 hours from Insulin Glargine administration (percentage).

IV. DATA COLLECTION

For the control group, the data will be collected retrospectively and recorded in standardized DCS in RedCap. For the intervention group, the data will be collected prospectively by the investigator team members and observations will be recorded in standardized DCS in RedCap. All protected health information (PHI) will be de-identified for both intervention and control group by using de-identification function in REDCap.

V. DATA ANALYSIS

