The sample size calculation considered the average time of AG closure in the last 3 months in FV-MICU was 15.6 ± 2.5 hours (CI 95%) and SD of 6 hours. Using one-sided α of 0.025 and an β of 0.10, an expected 20% difference between the two groups, a sample size of 160 totally of the participant will be adequate.

Categorical variables will be described as frequency rates and percentages, and continuous variables will be described using mean, median, and interquartile range (IQR). Proportions for categorical variables will be compared by Chi-squared test of Fisher's exact test. Means for continuous variables will be compared by Student's t-test if normally distributed and Mann-Whitney test if not normally distributed. All statistical analyses will be performed with a one-sided p-value < 0.025 to determine statistical significance. All statistical analyses will be completed by study investigators using Statistical Analysis Software (SAS).

VI. DATA AND SAFETY MONITORING PLAN (if applicable)

All data will be stored in a secured REDcap database. No PHI will be saved on non-HIPAA protected devices. All protected health information (PHI) will be de-identified by using RedCap.

To ensure patient safety, CCF Hypoglycemia protocol is getting followed in all patients receiving insulin including our enrolled participants. Before IV insulin discontinuation, the blood glucose level is getting checked hourly as per protocol. Once the AG is closed and insulin infusion is discontinued, the patient who is maintaining oral intake, blood glucose will be checked with meals, bedtime, and 2 am. If the patient having poor oral intake, blood glucose will be checked q 4 hours. Different treatment options for any hypoglycemic events are available in the protocol depending on the severity of the hypoglycemia event and patient awareness, ranging from oral carbohydrate supplement to IV fluid containing dextrose.

VII. STUDY LIMITATIONS

- Retrospective EPIC data review for the control group. Single-center.

VIII. ETHICAL CONSIDERATIONS

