For patient safety, insulin therapy is carrying a risk of hypoglycemia events. Previous studies didn't show any additional risk when insulin glargine has been given before anion gap closure comparing to the common practice, after anion gap closure. Shankar and Hsia's studies (4, 8) didn't reveal any hypoglycemic events between both groups. Both Doshi and Houshyar's studies (6, 7) revealed similar hypoglycemic events between both intervention and control groups and were neither clinically nor statistically significant.

The possible explanation for that is although the overlap time of glargine and IV insulin infusion is longer in the intervention group, the insulin infusion rate is getting adjusted hourly to meet the body requirement to decrease the blood sugar by a range of 50 - 100 mg/dl per hour. To ensure patient safety, CCF Hypoglycemia protocol is getting followed in all patients receiving insulin including our enrolled participants. Before IV insulin discontinuation, the blood glucose level is getting checked hourly as per protocol. Once the AG is closed and insulin infusion is discontinued, the patient who is maintaining oral intake, blood glucose will be checked with meals, bedtime, and 2 am. If the patient having poor oral intake, blood glucose will be checked q 4 hours. Different treatment options for any hypoglycemic events are available in the protocol depending on the severity of the hypoglycemia event and patient awareness, ranging from oral carbohydrate supplement to IV fluid containing dextrose. After AG closure the pre meals and correctional insulin doses will be left to the treating physician's discretion.

For data safety, all data will remain anonymous, and no personal health information will be associated with any data resulting from this study. Data will recorded directly into a secure REDCap database. No PHI will be saved on non-HIPAA protected devices. All protected health information (PHI) will be de-identified by using RedCap.

All subjects will be provided a consent form describing this study and with sufficient information to make an informed decision about participation in the study. The consent form will be submitted with the protocol for review and approval by the IRB. The formal consent of a subject, using the IRB-

approved consent form, will be obtained before the subject undergoes any study procedure. This consent form must be signed by the subject, and the investigator-designated research staff obtaining the consent.

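### The hypoglycemia comparison starts its 24-hour clock at glargine, so the two groups are observed in different phases of DKA care and the effect of early glargine cannot be isolated

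*Combined protocol and SAP*

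**What the plan says.** Section III.D defines the outcome as "Incidence of hypoglycemia (defined as ≤ 70 mg/dL, <54, <40) during 24 hours from Insulin Glargine administration (percentage"; section III.A gives the same window. The data sheet in section III.C follows it, with a field for "Hypoglycemia event within 24 hrs from glargine".

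The outcome is meant for a comparison. Section III.A states "Clinical outcomes will be compared between the intervention and control groups", and section V adds "Proportions for categorical variables will be compared by Chi-squared test" or Fisher's exact test, without adjustment.

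The start of the window differs by group. Intervention patients receive glargine no later than 4 h after IVII start (sections III.A and III.C). Controls are historical patients who "didn't receive basal insulin before AG closure" (section III.C). Section VIII acknowledges that "the overlap time of glargine and IV insulin infusion is longer in the intervention group".

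Glucose monitoring also changes with phase. Section VI says "Before IV insulin discontinuation, the blood glucose level is getting checked hourly as per protocol". Afterwards, checks fall to meals, bedtime and 2 am, or every 4 h if oral intake is poor.

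Hyperglycemia above 180 mg/dL has the same 24-hour glargine window in section III.D, but its data-sheet field is tied to the 24 h after IVII discontinuation.

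**The concern.** A window that opens at glargine opens early in the infusion for one group and at or after AG closure for the other. Three things follow.

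- Hypoglycemia in a control while on the infusion, before glargine, is never counted. The same phase is counted in the intervention group as soon as glargine is given.
- Hourly checking fills much of the intervention window and little or none of the control window, so the chance of detecting a low value differs.
- The documents do not say that every control received glargine. A control given another basal insulin, or none, has no defined window.

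This is the only hypoglycemia outcome listed, and it bears on Specific Aim 2 (safety). A difference between groups, or the absence of one, would mix glargine timing with treatment phase and detection. Matching on baseline characteristics and DKA severity does not touch this, and the limitations in section VII do not mention it.

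**Working it through.** **Inputs.** Section V: mean time to AG closure 15.6 h, SD 6 h, planned 20% effect, one-sided α 0.025, β 0.10, N = 160. Sections III.A and VI: hourly checks on IVII, then about 5 a day (three meals, bedtime, 2 am) or 6 a day (every 4 h). Glargine at g = 0 to 4 h after IVII start in the intervention group.

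**The plan's own figure.** The effect is 0.20 × 15.6 = 3.12 h. Then n = 2 × (1.960 + 1.282)² × 6² / 3.12² = 77.7, so 78 per group and 156 in total with equal groups (assumed). This is consistent with 160. The plan gives no figure for hypoglycemia.

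**Assumptions for the illustration.** Closure is timed from IVII start (the plan does not state the origin). The 15.6 h average applies to controls. IVII stops at closure unless overlap is stated. The written check schedule applied to the historical controls. Control glargine is given at closure, with 0, 2 or 4 h of infusion afterwards (assumed; the documents give no overlap length).

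**Infusion hours inside the 24-h window.** Intervention closure under the planned effect is 0.8 × 15.6 = 12.48 h.
- Intervention: 12.48 − g = 8.48 to 12.48 h. With no effect: 15.6 − g = 11.6 to 15.6 h.
- Control: 0, 2 or 4 h.

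**Scheduled checks in the window** = on + (24 − on) × r/24, where on is the infusion hours in the window and r is 5 or 6 a day.

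| Group | Hours on IVII | r = 5 | r = 6 |
|---|---|---|---|
| Intervention, planned effect, g = 4 | 8.48 | 11.7 | 12.4 |
| Intervention, planned effect, g = 0 | 12.48 | 14.9 | 15.4 |
| Intervention, no effect, g = 4 | 11.6 | 14.2 | 14.7 |
| Intervention, no effect, g = 0 | 15.6 | 17.4 | 17.7 |
| Control, no overlap | 0 | 5.0 | 6.0 |
| Control, 2 h overlap | 2 | 6.6 | 7.5 |
| Control, 4 h overlap | 4 | 8.2 | 9.0 |

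With the same r in both groups, the ratio under the planned effect runs from 12.36/9.0 = 1.4 to 14.88/5.0 = 3.0. With no effect on closure it reaches 17.35/5.0 = 3.5.

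**Shared time.** On the clock from IVII start, the windows share 24 + g − c hours, where c is control closure. At c = 15.6 this is 8.4 to 12.4 of 24 h. One SD either way (c = 9.6 to 21.6) gives 2.4 to 18.4 h.

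**Can the definition alone create a difference?** Suppose glargine timing has no effect, closure is at 15.6 h in both groups and g = 4. The intervention window then has 11.6 h on IVII and 12.4 h off it; the control window has 24 h off it. The hourly hazards below are assumed.
- 0.010 on IVII, 0.005 after: 1 − exp(−0.178) = 16.3% against 1 − exp(−0.120) = 11.3%.
- 0.005 on IVII, 0.010 after: 1 − exp(−0.182) = 16.6% against 1 − exp(−0.240) = 21.3%.
- Equal hazards of 0.005: 11.3% in both.

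The artefact can take either sign.

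**A common 0-48 h window from IVII start.** Checks = on + (48 − on) × r/24, under the planned effect.
- Intervention (on = 12.48): 19.9 to 21.4.
- Control: 22.3 to 23.7 with no overlap (on = 15.6); 25.5 to 26.7 with 4 h overlap (on = 19.6).
- Ratio: 19.88/25.52 = 0.78 to 21.36/23.7 = 0.90.

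Under a normal model with SD 6 h, the share with less than 24 h left after closure is 1 − Φ((24 − 15.6)/6) = 8.1% of controls and 1 − Φ((24 − 12.48)/6) = 2.7% of intervention patients.

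**The case against.** Aim 2 names no comparator, and the 24 h after glargine is a natural period in which to describe the safety of that dose. This stands for a description of the intervention group. It does not rescue the comparison that sections III.A and V plan.

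It can also be argued that the present window errs on the safe side, since more checks favour finding hypoglycemia in the intervention group. That is fair for detection alone. A reader might infer that the net bias runs against early glargine, but the documents give no hypoglycemia risk by phase, and the assumed hazards above produce either sign.

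For hyperglycemia, a reader might infer that the glargine clock inflates the intervention count, because that window can open while presenting glucose is still high. The documents do not support this. They give no distribution of presenting glucose, and section VIII only states a target to "decrease the blood sugar by a range of 50 - 100 mg/dl per hour". The introduction cites rebound hyperglycemia of 93.5% in controls against 33.3% with glargine, and a control window opening at or after closure covers that rebound phase. The direction is unknown. Nor does a 180 mg/dL cutoff contradict the glucose targets in section III.A: an outcome threshold need not equal a treatment target. The mean or median glucose over the stay (section III.B) is a separate measure that does not use the glargine clock.

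Finally, 0-48 h is a choice with drawbacks of its own, which are set out with the change below.

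**Conclusion.** The point holds. The mismatch follows from the group definitions and needs no numerical assumption: as written, the between-group hypoglycemia comparison cannot isolate the effect of early glargine, and the direction of net bias is not determined by the documents.

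The size is illustrative. On the assumptions listed, the intervention window holds about 12-15 scheduled checks under the planned effect, or 14-18 with none. The control window holds 5-6, or about 7-9 with an assumed 2-4 h of overlap. The windows share about 8-12 of 24 h when a control closes at 15.6 h, with wide variation between patients.

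Hyperglycemia has the same clock problem, again of unknown direction, and a narrower inconsistency between its outcome anchor (glargine) and its data-sheet anchor (IVII discontinuation). This should be fixed before control data are abstracted.

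**What to change.** 1. **Hypoglycemia.** Make the between-group outcome the incidence over one fixed period from IVII start in both groups, for example 0-48 h. Report it separately during and after IVII, with the number of glucose checks per group. Add another fixed length as a sensitivity analysis: 0-28 h contains every intervention patient's full 24 h after glargine, while 0-60 h covers late closers better. Keep the 24-h post-glargine rate as a description of the intervention group only.
2. **Hyperglycemia.** Use the data sheet's 24 h after IVII discontinuation as the between-group window and bring section III.D into line with it. The mean or median over the stay can remain as a separate measure.

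**Cost.** N = 160 is unchanged, and IVII start and stop, glargine and closure times are already recorded. The hypoglycemia field is limited to 24 h from glargine, so it must be widened, and a check count added. Extra glucose abstraction is needed in both groups: control events before glargine, and intervention events before glargine and beyond 24 h after it.

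**Downsides.** Over 0-48 h the check ratio of about 0.78-0.90 under the planned effect means fewer checks in the intervention group, which could make early glargine look safer. The during/after split and the check counts are there to expose this. A longer window takes in more discretionary later insulin and may dilute a timing effect. Some late closers (8.1% of controls and 2.7% of intervention patients on the normal model) and patients discharged before 48 h are incompletely covered; their number should be reported.

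### The six ordered glucose bands in III.B fall under a chi-squared rule in V which, applied to one table, ignores their order and cannot be one-sided

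*Combined protocol and SAP*

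**What the plan says.** Section III.B (definition of main exposures and outcomes) announces a comparison, not only a description: "For the hyperglycemia analysis, patients will be compared in the following categories according to their mean or median". Six bands follow, rising from below 80 mg/dL to a last band printed as "Mean/median BG > 240 mg/dL".

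Section V (data analysis) gives one rule for categorical data: "Proportions for categorical variables will be compared by Chi-squared test", with Fisher's exact test named in the same sentence (I read the word joining the two as a slip for or). For continuous data it says: "Means for continuous variables will be compared by Student's t-test if normally distributed and Mann-Whitney test if not normally distributed". It then sets one threshold for everything: "All statistical analyses will be performed with a one-sided p-value < 0.025 to determine statistical significance".

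No trend, rank or ordinal method is assigned to the bands. Section III.D does not list the bands as an outcome. Its hyperglycemia outcome is the incidence of glucose above 180 mg/dL in the 24 hours from glargine.

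**The concern.** The bands carry an order, and the rule that covers them does not use it. Chi-squared and Fisher's exact test on a table with two rows and six columns treat the columns as unordered labels. This has three consequences:

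- A real downward shift in glucose is harder to detect than it need be.
- The one-sided threshold has no meaning for this analysis. The analyst would have to choose between 0.05 and 0.025 for a non-directional p-value, possibly after seeing the data.
- A significant result shows only that the two distributions differ. It could reflect higher glucose on glargine or a change of shape.

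The per-patient mean or median has to be calculated before a patient can be placed in a band, so a better variable is already at hand.

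**Working it through.** **Inputs.** From section V: control mean 15.6 h, SD 6 h, a 20% difference, one-sided α 0.025, β 0.10, total 160. From III.B: the band limits. Assumed, because the documents do not say: 1:1 allocation (80 per group), bands made exclusive at 80/100/140/180/240, and normally distributed per-patient glucose.

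**1. The plan's own figure.** δ = 0.20 × 15.6 = 3.12 h. n per group = 2(z₀.₉₇₅ + z₀.₉₀)²σ²/δ² = 2 × (1.960 + 1.282)² × 36 / 3.12² ≈ 77.7, so 78 per group and 156 in total, against 160 stated. The figure is reproduced; 80 per group gives 90.8% power. It applies to anion gap closure. The plan gives no power for the bands.

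**2. Structure of the test.** X² = Σ(O − E)²/E, with (2 − 1)(6 − 1) = 5 degrees of freedom (df). Reordering the columns leaves the sum unchanged, and squaring removes the sign. In a 2×2 table X² is the square of a z-statistic, so direction can be recovered. With more than 1 df it cannot.

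**3. Analytic loss.** Suppose all the signal lies in the ordered direction. An ordered 1-df test with 90% power has noncentrality (1.960 + 1.282)² ≈ 10.5. Spreading that over more df gives:

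| df in use | chi-squared at 0.05 | chi-squared at 0.025 |
|---|---|---|
| 2 | 84% | 76% |
| 3 | 78% | 69% |
| 4 | 74% | 64% |
| 5 | 70% | 60% |

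Starting from 80% power, the 5-df test has 56% at 0.05 and 44% at 0.025. Equal power with 5 df needs about 1.6 times the sample size (1.57 to 1.63).

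**4. Simulation.** 20,000 replicates, 80 per group, control mean 140 to 210 mg/dL, SD 20 to 60, downward shift 0.35 to 0.52 SD. Examples:

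| Control mean, SD | Shift (SD) | chi-squared 0.05 | chi-squared 0.025 | Rank-sum on bands, one-sided 0.025 | Loss at 0.05 (points) |
|---|---|---|---|---|---|
| 180, 40 | 0.45 | 0.463 | 0.343 | 0.745 | 28 |
| 180, 60 | 0.45 | 0.505 | 0.387 | 0.764 | 26 |
| 180, 60 | 0.52 | 0.654 | 0.537 | 0.874 | 22 |
| 210, 40 | 0.45 | 0.510 | 0.387 | 0.737 | 23 |
| 190, 25 | 0.35 | 0.290 | 0.193 | 0.457 | 17 |
| 170, 20 | 0.35 | 0.360 | 0.259 | 0.466 | 11 |

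The loss is 22 to 28 points where the bands are well filled (SD 40 to 60, mean 140 to 200). It is 17 to 23 at SD 25 to 40 with mean 190 to 210. It is 11 to 12 at SD 20, where only about two df are in use. A t-test on the ungrouped value has 0.812 at a 0.45 SD shift.

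**5. Direction.** Reverse the shift so that glucose rises on glargine (mean 180, SD 60, up by 0.45 × 60 = 27 mg/dL). Chi-squared rejects in 49% of replicates at 0.05 and 37% at 0.025. The one-sided ordered tests reject in about 0%.

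**6. Where chi-squared does better.** Keep the mean at 160 and narrow the SD from 60 to 40. Chi-squared at 0.05 rejects in 62%, the one-sided rank-sum test in 2%.

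**The case against.** **The single table is an inference.** No sentence in the plan sets up one six-column table. As printed the bands cannot form one, because above 180 contains above 240. Nested limits suit another reading, in which each band is a yes/no proportion, as the three hypoglycemia thresholds in III.B are. Each test would then be a 2×2 with a direction, and the one-sided rule would apply. This stands, so the point is conditional. That reading still would not use the order: cutting at 180 alone gives 0.61 power at mean 180, SD 60, shift 0.45 SD, against 0.764 for the rank-sum test.

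**The loss could be overstated.** A reader might take the widest gap as the price of ignoring order. For 190 against 170 mg/dL with SD 40, chi-squared at 0.025 has 44% power and a t-test on the raw value 88%, a gap of 44 points. That gap mixes three things: order (83 − 57 = 26), an assumed stricter threshold (57 − 44 = 13) and the grouping itself (88 − 83 = 5). Only the first belongs to the unordered test, and the documents supply no distribution that would fix its size.

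**Sparse bands.** With mean 180 and SD 40 the two lowest control bands expect 80 × 0.006 ≈ 0.5 and 80 × 0.017 ≈ 1.4 patients, so Fisher's exact test might be used. It is equally unordered, but its power was not simulated.

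**Ordered tests have a cost.** Step 6 shows it. A one-sided ordered test also counts a move into the lowest band as improvement, and hypoglycemia safety is Specific Aim 2. This stands and should be stated in the plan.

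**Conclusion.** The concern holds in a limited form. If the bands are tested as one table under the rule in V, the test ignores their order and has no direction, and the one-sided 0.025 rule cannot be carried out. That part needs no assumed data.

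The size does rest on assumptions: 80 per group, exclusive bands, and a shift in normally distributed per-patient glucose. On these, chi-squared at 0.05 loses roughly 11 to 28 points of power against a one-sided rank-sum test on the same bands, and holding its p-value to 0.025 costs about 8 to 13 more. The advantage of ordered tests applies to a shift, not to a change in spread.

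A reader might infer that the trial's hyperglycemia conclusion is compromised. The documents do not support that. The bands are a supportive analysis, and the listed hyperglycemia outcome is binary and can be tested one-sided. The primary outcome, the sample size and the hypoglycemia outcomes are untouched. This is a cheap improvement, not a threat to the main result.

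**What to change.** In section V, state that each patient's mean or median glucose will be compared as a continuous variable with the t-test or Mann-Whitney test already named there, at one-sided 0.025, and that the band table is descriptive.

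If the bands are to be tested, first make them mutually exclusive (the top two overlap, and exactly 80 mg/dL falls in none). Then name a rank-sum or Cochran-Armitage trend test at one-sided 0.025.

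Either way, add that the test is insensitive to a change in spread and counts movement into the lowest band as improvement, so the low end will be judged by the separate hypoglycemia outcomes.

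The cost is a sentence or two in V, plus corrected band limits in III.B if the bands are tested. No new data or patients are needed.

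### The historical-control comparison has no planned adjusted or matched outcome analysis, and the matching it relies on is not specified

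*Combined protocol and SAP*

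**What the plan says.** The combined protocol and SAP describes a prospective, open-label intervention cohort (Section III.A). The intervention group is patients who "meet the inclusion criteria and accepted to receive insulin glargine early as per the protocol" (Section III.C). Controls are DKA admissions to the same unit from 1 January 2019 "till the IRB approval date and didn't receive basal insulin before AG closure" (Section III.C), with data taken retrospectively from charts.

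On comparability, Section III.A says: "Prespecified sample size and matched in basal patient characteristics and DKA severity will be selected as the control group". Section III.C describes the controls as consecutive and speaks of a matched sample size.

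Section III.B introduces mild, moderate and severe classes by arterial pH and bicarbonate ("DKA classification as the following table from ADA"). It does not say that this table is the matching criterion.

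Section V gives the tests. For continuous variables, "Means for continuous variables will be compared by Student's t-test if normally distributed and Mann-Whitney test if not normally distributed"; for proportions, chi-squared or Fisher's exact. No regression, stratified, propensity or paired method appears. The study variables in Section III.C include many baseline items, among them initial "Anion gap (mEq/L", but no use of them in an outcome analysis is stated. Section VII lists retrospective control data and a single center as limitations; it does not name confounding.

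**The concern.** In a non-randomized comparison the two groups can differ in prognosis before treatment starts. Here they differ by design in calendar period, in consent, and in how they were selected: controls are chosen partly on not having received basal insulin before closure, which is known only after baseline. An unadjusted test attributes the whole difference in closure time to glargine.

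Initial anion gap matters most clearly. The outcome is the time for the gap to fall to 12 or below, so the initial gap is its starting point. If the glargine group starts with a lower gap, it would be expected to close sooner whatever the treatment does. The descriptive comparisons in Section V could be read to cover baseline variables, so an imbalance might be noticed. No stated outcome analysis would then correct it.

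An unspecified match also leaves open which controls are chosen, including after closure times have been seen. The primary efficacy claim (Specific Aim 1) rests entirely on this comparison.

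**Working it through.** **Inputs.** From Section V: control mean 15.6 h, SD 6 h, 20% difference, one-sided alpha 0.025, beta 0.10, total 160. Assumed: 80 per arm, since no ratio is stated.

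**The plan's own figure.** Target difference: 0.20 × 15.6 = 3.12 h. Patients per arm: 2 × [6 × (1.960 + 1.282) / 3.12]² = 77.7, so 78, or 156 in total (158 with the t distribution). Power at 80 per arm is 90.8% (normal) or 90.5% (t). The stated 160 is therefore sound on its inputs, and it corresponds to an unadjusted comparison of two independent groups.

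**Tolerance to residual bias (illustration only).** SE = 6 × √(2/80) = 0.949 h. With no true effect and a bias of b hours toward glargine, the one-sided error is 1 − Φ(1.960 − b/SE). With the same bias against glargine, power is Φ((3.12 − b)/SE − 1.960).

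| b (h) | b/SE | Error if toward glargine | Power if against |
|---|---|---|---|
| 0 | 0 | 2.5% | 91% |
| 0.30 | 0.316 | 5.0% | 84% |
| 0.75 | 0.791 | 12.1% | 70% |
| 1.00 | 1.054 | 18% | 61% |

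The bias that doubles the error is (1.960 − 1.645) × 0.949 = 0.299 h, about 18 minutes, or 0.299/3.12 = 9.6% of the target.

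**Would a baseline test reveal the imbalance?** For a standardized imbalance of 0.25 SD, 0.25/√(2/80) = 1.581, and 1 − Φ(1.960 − 1.581) = 35%. A non-significant baseline test is weak reassurance.

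**Can the severity table carry the matching?** Setting the sections side by side:
- The table uses pH and bicarbonate and does not contain the anion gap.
- Eligibility is "Diagnosis of DKA will be made by ICD-10-CM code E10.10, E11.10, or meeting the ADA definition", the latter being glucose, anion gap and ketones. It sets no pH or bicarbonate limit. The table stops at pH 7.30 and bicarbonate 18, so an eligible patient may have no class.
- No rule covers pH and bicarbonate that point to different classes.
- Arterial pH is absent from the listed initial laboratory values. The data collection sheet in the appendix is not shown and could not be checked.

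**Precision of an adjusted analysis (raw hours, n = 160).** Nine covariate coefficients: anion gap, bicarbonate, glucose, age, weight, diabetes type and home basal insulin (one each), and precipitant (two, if grouped into three levels). With group and intercept, 160 − 11 = 149 residual df. Let R² be the outcome variance explained by the covariates and g the share of group membership that they explain. Adjusted SE = 0.949 × √[(1 − R²)/(1 − g)]; power for 3.12 h from the noncentral t:

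| g | R² = 0 | R² = 0.10 | R² = 0.25 |
|---|---|---|---|
| 9/159 (chance only) | 89% | 92% | 96% |
| 0.20 (assumed) | 83% | 87% | 92% |
| 0.30 (assumed) | 78% | 82% | 88% |

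**The case against.** **Matching is planned.** This is true and deserves credit. Baseline characteristics could include initial anion gap, and the equal-groups reading of Section III.C together with the reproduced 160 makes a 1:1 ratio plausible. Drawing controls from a consecutive list is also a partial safeguard, although consecutive and matched selection need reconciling. What stands against it is that none of this is fixed, so the match cannot be reproduced or judged.

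**Unpaired tests on matched data are conservative.** If pairs were correlated at 0.3, the actual one-sided error would be about 1.0%. That concerns variance; it does not remove bias from factors left unbalanced.

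**The bias figures are arithmetic, not evidence.** This stands. They would hold for any unrandomized study with this SE, and they show neither that a bias exists nor which way it runs.

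**A stronger reading.** A reader might infer that matching on the three severity classes would leave a calculable share of any anion-gap difference, with a matching false-positive rate. The documents do not support this. They never say that the table is the matching criterion, they do not exclude initial anion gap from the match, and they give no correlations. Any such share depends entirely on assumptions.

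**Conclusion.** The point holds. The planned primary comparison is non-randomized, its stated tests are unadjusted, and its one safeguard is an unspecified match, so any imbalance that survives matching enters the glargine estimate uncorrected. This should be resolved before outcome data are analyzed.

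The size is conditional. At 80 per arm (assumed) and SD 6 h (from the plan), 0.30 h of residual bias toward glargine doubles the one-sided error, and 0.75 h raises it to 12%. The documents do not show that a bias of either size will occur. The conclusion does not depend on a particular value, because no planned outcome analysis would correct an imbalance of any size.

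Two further inferences should be avoided. Adjustment does not make this comparison equivalent to a randomized one; it addresses only bias that runs through measured covariates. And the power figures for the adjusted analysis are on raw hours, so they are not the power of a log-scale primary analysis.

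**What to change.** **Primary analysis.** Prespecify one adjusted analysis of time to anion gap closure, with the outcome scale fixed in advance: regression on group with initial anion gap, bicarbonate, glucose, age, weight, diabetes type, precipitant (grouping stated, since eight causes are listed) and home basal insulin use. All are already on the variable list. Add a missing-covariate rule that also covers the unknown answer under "Using Basal insulin at home (Yes/No/ unknown". Keep the unadjusted test as supportive. A fully specified propensity or matched-set analysis, named as primary in advance, would also serve.

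**Matching.** Name the variables, including initial anion gap, with tolerance and ratio. Select controls by a fixed algorithm before closure times are abstracted, and report standardized differences. Reconcile the consecutive-controls and matched-sample-size wording in Section III.C with the matched selection in Section III.A. If the severity table is used, say how patients outside it, or with discordant values, are classed, and add pH to the variable list.

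**Limitations.** Name confounding, and state that adjustment cannot remove calendar-period, consent or control-selection differences.

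**Cost.** Plan wording, modest programming, handling of missing chart data, and some precision if covariates differ systematically between groups. On raw hours, power for 3.12 h is about 89%–96% under chance imbalance. It is about 83%–92% or 78%–88% if covariates explain an assumed 20% or 30% of group membership (R² from 0 to 0.25 throughout). The unadjusted figure is 90%.
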